10.1.8 Study and Site Closure

The Sponsor designee reserves the right to close the study site or terminate the study at any time for any reason at the sole discretion of the Sponsor. Study sites will be closed upon study

completion. A study site is considered closed when all required documents and study supplies have been collected and a study-site closure visit has been performed.

The Investigator may initiate study-site closure at any time, provided there is reasonable cause and sufficient notice is given in advance of the intended termination.

Reasons for the early closure of a study site by the Sponsor or Investigator may include but are not limited to:

- Failure of the Investigator to comply with the protocol, the requirements of the IRB/IEC or local health authorities, the Sponsor's procedures, or GCP guidelines
- Inadequate recruitment of participants by the Investigator
- Discontinuation of further bimekizumab development

10.1.9 Publication Policy

The results of this study may be published or presented at scientific meetings. If this is foreseen, the Investigator agrees to submit all manuscripts or abstracts to the Sponsor before submission. This allows the Sponsor to protect proprietary information and to provide comments.

The Sponsor will comply with the requirements for publication of study results. In accordance with standard editorial and ethical practice, the Sponsor will generally support publication of multicenter studies only in their entirety and not as individual site data. In this case, a coordinating Investigator will be designated by mutual agreement.

Authorship will be determined by mutual agreement and in line with International Committee of Medical Journal Editors authorship requirements.

10.2 Appendix 2: Clinical laboratory tests

- The tests detailed in the table below will be performed by the central laboratory.
- Protocol-specific requirements for inclusion or exclusion of participants are detailed in Section 5.1 and Section 5.2 of the protocol.
- Additional tests may be performed at any time during the study as determined necessary by the Investigator or required by local regulations.

Protocol-Required Safety Laboratory Assessments

Laboratory Assessments	Parameters			
Hematology	Platelet Count	RBC Indices: Mean corpuscular hemoglobin Mean corpuscular hemoglobin concentration Mean corpuscular volume		White Blood Cell Count with Differential: Neutrophils Lymphocytes Atypical lymphocytes Monocytes Eosinophils Basophils
	RBC Count			
	Hemoglobin			
	Hematocrit			
Clinical Chemistry	Blood urea nitrogen	Potassium	Alanine aminotransferase ^a	Total and direct bilirubin ^{a,b}
	Creatinine	Sodium	Aspartate aminotransferase ^a	Glucose (record fasting or nonfasting in CRF)
	Bicarbonate	Calcium	Alkaline phosphatase	Gamma glutamyltransferase
	Uric acid	Chloride	Magnesium	hs-CRP ^c
	Lactate dehydrogenase	Total cholesterol		
Routine Urinalysis	Specific gravity pH, glucose, protein, ketones, nitrite, blood by dipstick Microscopic examination (if blood or protein is abnormal)			
Other Screening Tests	Pregnancy testing ^d Follicle stimulating hormone ^e Urine drug screen (amphetamines, barbiturates, cocaine, opiates, cannabinoids, and benzodiazepines) Serology (human immunodeficiency virus, Hepatitis B, Hepatitis C)			

Protocol-Required Safety Laboratory Assessments

ALT=alanine aminotransferase; AST=aspartate aminotransferase; CRF=case report form;

hs-CRP=high-sensitivity C-reactive protein; RBC=red blood cell; ULN=upper limit of normal

^a Details of liver chemistry stopping criteria and required actions and follow-up assessments after liver stopping or monitoring event are given in Section 7.1.2 and Appendix 6 (Section 10.6). All events of $\geq 3 \times$ ULN ALT or AST with coexisting $\geq 2 \times$ ULN total bilirubin in the absence of $\geq 2 \times$ ULN alkaline phosphatase, with no alternative explanation for the biochemical abnormality may indicate severe liver injury (possible Hy's Law) and must be reported as an SAE (excluding studies of hepatic impairment or cirrhosis).

^b If total bilirubin is $>$ ULN, a direct bilirubin estimation (%) will be performed.

^c hs-CRP will be tested at specified visits (Table 1-1).

^d A serum pregnancy test will be performed at Screening for all women of childbearing potential. A urine pregnancy test (urine dipstick analyzed locally) is also required at the Baseline Visit and all other visits in the Schedule of Activities (Table 1-1). Pregnancy test results must be negative prior to administering IMP.

^e A high follicle stimulating hormone level in the postmenopausal range may be used to confirm a postmenopausal state in women not using hormonal contraception or hormonal replacement therapy. However, in the absence of 12 months of amenorrhea, a single follicle stimulating hormone measurement is insufficient.

Investigators must document his or her review of each laboratory safety report.

Laboratory and/or analyte results (eg, hs-CRP, immunogenicity, PK) that could unblind the study will not be reported to any blinded study personnel as long as the study remains blinded.

10.3 Appendix 3: Adverse events – definitions and procedures for recording, evaluating, follow-up, and reporting

Definition of AE

AE Definition

• An AE is any untoward medical occurrence in a patient or clinical study participant, temporally associated with the use of IMP, whether or not considered related to the IMP.• Note: An AE can therefore be any unfavorable and unintended sign (including an abnormal laboratory finding), symptom, or disease (new or exacerbated) temporally associated with the use of IMP.

Events Meeting the AE Definition

• Any abnormal laboratory test results (hematology, clinical chemistry, or urinalysis) or other safety assessments (eg, ECG, radiological scans, vital signs measurements), including those that worsen from Baseline, considered clinically significant in the medical and scientific judgment of the Investigator (ie, not related to progression of underlying disease).• Exacerbation of a chronic or intermittent pre-existing condition including either an increase in frequency and/or intensity of the condition.• New conditions detected or diagnosed after IMP administration even though it may have been present before the start of the study.• Signs, symptoms, or the clinical sequelae of a suspected drug-drug interaction.• Signs, symptoms, or the clinical sequelae of a suspected overdose of either IMP or a concomitant medication. Overdose per se will not be reported as an AE/SAE unless it is an intentional overdose taken with possible suicidal/self-harming intent. Such overdoses should be reported regardless of sequelae.• "Lack of efficacy" or "failure of expected pharmacological action" per se will not be reported as an AE or SAE. Such instances will be captured in the efficacy assessments. However, the signs, symptoms, and/or clinical sequelae resulting from lack of efficacy will be reported as AE or SAE if they fulfil the definition of an AE or SAE.

Events NOT Meeting the AE Definition

- Any clinically significant abnormal laboratory findings or other abnormal safety assessments which are associated with the underlying disease, unless judged by the Investigator to be more severe than expected for the participant's condition.
- The disease/disorder being studied or expected progression, signs, or symptoms of the disease/disorder being studied, unless more severe than expected for the study participant's condition.
- Medical or surgical procedure (eg, endoscopy, appendectomy): the condition that leads to the procedure is the AE.
- Situations in which an untoward medical occurrence did not occur (social and/or convenience admission to a hospital).
- Anticipated day-to-day fluctuations of pre-existing disease(s) or condition(s) present or detected at the start of the study that do not worsen.

PUBLIC COPY
This document cannot be used to support any marketing authorization application and any extensions or variations thereof.

Definition of SAE

If an event is not an AE per definition above, then it cannot be an SAE even if serious conditions are met (eg, hospitalization for signs/symptoms of the disease under study, death due to progression of disease).

A SAE is defined as any untoward medical occurrence that, at any dose:
a. Results in death
b. Is life-threatening The term 'life-threatening' in the definition of 'serious' refers to an event in which the participant was at risk of death at the time of the event. It does not refer to an event, which hypothetically might have caused death, if it were more severe.
c. Requires inpatient hospitalization or prolongation of existing hospitalization In general, hospitalization signifies that the participant has been detained (usually involving at least an overnight stay) at the hospital or emergency ward for observation and/or treatment that would not have been appropriate in the physician's office or outpatient setting. Complications that occur during hospitalization are AEs. If a complication prolongs hospitalization or fulfills any other serious criteria, the event is serious. When in doubt as to whether "hospitalization" occurred or was necessary, the AE should be considered serious. Hospitalization for elective treatment of a pre-existing condition that did not worsen from Baseline is not considered an AE.
d. Results in persistent disability/incapacity 
• The term disability means a substantial disruption of a person's ability to conduct normal life functions.• This definition is not intended to include experiences of relatively minor medical significance such as uncomplicated headache, nausea, vomiting, diarrhea, influenza, and accidental trauma (eg, sprained ankle) which may interfere with or prevent everyday life functions but do not constitute a substantial disruption.
e. Is a congenital anomaly/birth defect
f. Important medical events: 
• Medical or scientific judgment should be exercised in deciding whether SAE reporting is appropriate in other situations such as important medical events that may not be immediately life-threatening or result in death or hospitalization but may jeopardize the participant or may require medical or surgical intervention to prevent one of the other outcomes listed in the above definition. These events should usually be considered serious.• Examples of such events include, but are not limited to, potential Hy's law, invasive or malignant cancers, intensive treatment in an emergency room or at home for allergic bronchospasm, blood dyscrasias or convulsions that do not result in hospitalization, or development of drug dependency or drug abuse.

Recording and Follow-Up of AE and/or SAE

AE and SAE Recording

• When an AE/SAE occurs, it is the responsibility of the Investigator to review all documentation (eg, hospital progress notes, laboratory reports, and diagnostics reports) related to the event.• The Investigator will then record all relevant AE/SAE information in the CRF.• It is not acceptable for the Investigator to send photocopies of the participant's medical records to UCB in lieu of completion of the AE/SAE CRF page.• There may be instances when copies of medical records for certain cases are requested by UCB. In this case, all participant identifiers, with the exception of the participant number, will be redacted on the copies of the medical records before submission to UCB.• The Investigator will attempt to establish a diagnosis of the event based on signs, symptoms, and/or other clinical information. Whenever possible, the diagnosis (not the individual signs/symptoms) will be documented as the AE/SAE.
Assessment of Intensity

The Investigator will make an assessment of intensity for each AE and SAE reported during the study and assign it to 1 of the following categories:
 
• Mild: An event that is easily tolerated by the participant, causing minimal discomfort and not interfering with everyday activities.• Moderate: An event that causes sufficient discomfort and interferes with normal everyday activities.• Severe: An event that prevents normal everyday activities. An AE that is assessed as severe should not be confused with a SAE. Severe is a category utilized for rating the intensity of an event; and both AEs and SAEs can be assessed as severe.• An event is defined as 'serious' when it meets at least 1 of the predefined outcomes as described in the definition of an SAE, NOT when it is rated as severe (eg, a severe AE may be either serious or not serious, depending on whether these criteria are also met). 
The National Cancer Institute Common Terminology Criteria for Adverse Events (NCI-CTCAE) should be used as a supportive standardization instrument to evaluate AEs and SAEs but the final intensity grading by the Investigator must be mild, moderate, or severe.

Assessment of Causality

- The Investigator is obligated to assess the relationship between IMP and each occurrence of each AE/SAE.
- A "reasonable possibility" of a relationship conveys that there are facts, evidence, and/or arguments to suggest a causal relationship, rather than a relationship cannot be ruled out.
- The Investigator will use clinical judgment to determine the relationship.
- Alternative causes, such as underlying disease(s), concomitant therapy, and other risk factors, as well as the temporal relationship of the event to IMP administration will be considered and investigated.
- The Investigator will also consult the Investigator's Brochure and/or Product Information, for marketed products, in his or her assessment.
- For each AE/SAE, the Investigator **must** document in the medical notes that he or she has reviewed the AE/SAE and has provided an assessment of causality.
- There may be situations in which an SAE has occurred and the Investigator has minimal information to include in the initial report to UCB. However, **it is very important that the Investigator always make an assessment of causality for every event before the initial transmission of the SAE data to UCB.**
- The Investigator may change his or her opinion of causality in light of follow-up information and send a SAE follow-up report with the updated causality assessment.
- The causality assessment is one of the criteria used when determining regulatory reporting requirements.

Follow-up of AEs and SAEs

- The Investigator is obligated to perform or arrange for the conduct of supplemental measurements and/or evaluations as medically indicated or as requested by UCB to elucidate the nature and/or causality of the AE or SAE as fully as possible. This may include additional laboratory tests or investigations, histopathological examinations, or consultation with other health care professionals.
- An AE should be followed until it has resolved, has a stable sequelae, the Investigator determines that it is no longer clinically significant, or the participant is lost to follow up. This follow-up requirement applies to AEs, SAEs, and AEs of special interest.
- If a participant dies during participation in the study or during a recognized follow-up period, the Investigator will provide UCB with a copy of any post-mortem findings including histopathology.
- New or updated information will be recorded in the originally completed CRF.
- The Investigator will submit any updated SAE data to UCB within 24 hours of receipt of the information.

Reporting of SAEs

SAE Reporting to UCB via an Electronic Data Collection Tool

- The primary mechanism for reporting an SAE to UCB will be the electronic data collection tool.
- If the electronic system is unavailable for more than 24 hours, then the site will use the paper SAE data collection tool (see next section).
- The site will enter the SAE data into the electronic system as soon as it becomes available.
- After the study is completed at a given site, the electronic data collection tool will be taken off-line to prevent the entry of new data or changes to existing data.
- If a site receives a report of a new SAE from a study participant or receives updated data on a previously reported SAE after the electronic data collection tool has been taken off-line, then the site can report this information on a paper SAE form (see next section) or to the UCB study physician by telephone.
- Contacts for SAE reporting can be found on the page after the title page of this protocol.

SAE Reporting to UCB via Paper CRF

- Facsimile transmission of the SAE paper CRF is the preferred method to transmit this information to the Medical Monitor or UCB study physician.
- In rare circumstances and in the absence of facsimile equipment, notification by telephone is acceptable with a copy of the SAE data collection tool sent by overnight mail or courier service.
- Initial notification via telephone does not replace the need for the Investigator to complete and sign the SAE CRF pages within the designated reporting time frames.
- Contacts for SAE reporting can be found on the page after the title page of this protocol.

10.4 Appendix 4: Contraceptive guidance and collection of pregnancy information

Definitions

Woman of Childbearing Potential (WOCBP)

A woman is considered fertile following menarche and until becoming post-menopausal unless permanently sterile (see below).

Women in the following categories **are not considered WOCBP**:

1. Premenarchal
2. Premenopausal female with 1 of the following:
 - Documented hysterectomy
 - Documented bilateral salpingectomy
 - Documented bilateral oophorectomy

Note: Documentation can come from the site personnel's review of the participant's medical records, medical examination, or medical history interview.

3. Postmenopausal female
 - A postmenopausal state is defined as no menses for 12 months without an alternative medical cause. A high follicle stimulating hormone level in the postmenopausal range may be used to confirm a postmenopausal state in women not using hormonal contraception or hormonal replacement therapy (HRT). However, in the absence of 12 months of amenorrhea, a single follicle stimulating hormone measurement is insufficient.
 - Females on HRT and whose menopausal status is in doubt will be required to use one of the non-estrogen hormonal highly effective contraception methods if they wish to continue their HRT during the study. Otherwise, they must discontinue HRT to allow confirmation of postmenopausal status before study enrollment.

Contraception Guidance

Female participants of childbearing potential are eligible to participate if they agree to use a highly effective method of contraception consistently and correctly as described in the table below.

Highly Effective Contraceptive Methods^a

Highly Effective Contraceptive Methods That Are User Dependent^b

Failure rate of <1% per year when used consistently and correctly.

Combined (estrogen and progestogen containing) hormonal contraception associated with inhibition of ovulation

- Oral
- Intravaginal
- Transdermal

Progestogen only hormonal contraception associated with inhibition of ovulation

- Oral
- Injectable

Highly Effective Methods That Are User Independent

Implantable progestogen only hormonal contraception associated with inhibition of ovulation

- Intrauterine device
- Intrauterine hormone-releasing system
- Bilateral tubal occlusion

Vasectomized partner

A vasectomized partner is a highly effective contraception method provided that the partner is the sole male sexual partner of the WOCBP and the absence of sperm has been confirmed. If not, an additional highly effective method of contraception should be used.

Sexual abstinence

Sexual abstinence is considered a highly effective method only if defined as refraining from heterosexual intercourse during the entire period of risk associated with the IMP. The reliability of sexual abstinence needs to be evaluated in relation to the duration of the study and the preferred and usual lifestyle of the participant.

NOTES:

- a) In case of newly started contraception pills/intrauterine devices, Investigator should consider the correct timing of starting/applying such methods in relation to the menstrual cycle and the manufacturing instruction as when these newly started methods would become effective.
- b) Typical use failure rates may differ from those when used consistently and correctly. Use should be consistent with local regulations regarding the use of contraceptive methods for participants participating in clinical studies.

Pregnancy testing

- WOCBP should only be included after a confirmed menstrual period and a negative highly sensitive serum pregnancy test.
- Additional pregnancy testing should be performed as indicated in the Schedule of Activities (Table 1–1) during the treatment period and at 20 weeks after the last dose of IMP and as required locally.
- Pregnancy testing will be performed whenever a menstrual cycle is missed or when pregnancy is otherwise suspected

Male participants with partners who become pregnant

- The Investigator will attempt to collect pregnancy information on any male participant's female partner who becomes pregnant while the male participant is in this study. This applies only to male participants who receive IMP. If the study participant is later found to be on placebo, then pregnancy data collection can stop.
- In cases where the partner of a male subject enrolled in a clinical study becomes pregnant, the Investigator or designee is asked to contact the subject to request consent of the partner via the Partner Pregnancy Consent form that has been approved by the responsible IRB/IEC and should be available in the Investigator site file. In case of questions about the consent process, the Investigator may contact the UCB/CRO contract monitor for the study. The Investigator will complete the information in the eCRF only after the partner has agreed that additional information can be captured and has provided the signed Partner Pregnancy Consent form. UCB's Patient Safety department is also the primary contact for any questions related to the data collection for the partner pregnancy, eventual birth, and follow up.
- After obtaining the necessary signed informed consent from the pregnant female partner directly, the Investigator will record pregnancy information on the appropriate form and submit it to the Sponsor within 1 working day of learning of the partner's pregnancy. The female partner will also be followed to determine the outcome of the pregnancy. Information on the status of the mother and child will be forwarded to the Sponsor. Generally, the follow-up will be at least 12 months after the delivery date. Any termination of the pregnancy will be reported regardless of fetal status (presence or absence of anomalies) or indication for the procedure.

Female Participants who become pregnant

- Any female participant who becomes pregnant while participating in the study will discontinue IMP or be withdrawn from the study.
- The Investigator will collect pregnancy information on any female participant who becomes pregnant while participating in this study. Information will be recorded on the appropriate form and submitted to the Sponsor within 1 working day of learning of a participant's pregnancy. The participant will be followed to determine the outcome of the pregnancy. The Investigator will collect follow-up information on the participant and the neonate and the information will be forwarded to the Sponsor. Generally, the follow-up will be at least 12 months after the delivery date. Any termination of pregnancy will be reported, regardless of fetal status (presence or absence of anomalies) or indication for the procedure.
- While pregnancy itself is not considered to be an AE or SAE, any pregnancy complication or elective termination of a pregnancy will be reported as an AE or SAE. A spontaneous abortion is always considered to be an SAE and will be reported as such. Any post-study pregnancy related SAE considered reasonably related to the IMP by the Investigator will be reported to the Sponsor as described in Section 8.3.5. While the Investigator is not obligated to actively seek this information in former study participants, he or she may learn of an SAE through spontaneous reporting.

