4.1.2 Initial Treatment Period (Weeks 0-16) and Maintenance Treatment Period (Weeks 16-48)

Eligible study participants will be randomized in a 2:2:2:1 ratio as noted in the Study Schema to:

- Bimekizumab [REDACTED] from Weeks 0 to 48
- Bimekizumab [REDACTED] from Weeks 0 to 48
- Bimekizumab [REDACTED] to Week 16, continuing on [REDACTED] from Weeks 16 to 48
- Placebo to Week 16, continuing on bimekizumab [REDACTED] from Weeks 16 to 48

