The Maintenance Treatment Period is designed to assess the durability of response of the study endpoints and to provide sufficient longer-term (up to 48 weeks, including the Initial Treatment Period) safety and exposure to bimekizumab for regulatory filings. Continuous (up to 48 weeks) exposure to both the [REDACTED] bimekizumab [REDACTED] and [REDACTED] bimekizumab [REDACTED] dose regimens allow for the following assessments:

- Durability of response and longer-term safety
- Optimal dosing interval for maintenance treatment

This period will also allow study participants who received placebo in the Initial Treatment Period to begin receiving bimekizumab at Week 16 in the randomized, controlled Maintenance Treatment Period of the study.

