22. If study participant is using concomitant, non-opioid analgesics for HS-related or non-HS-related pain as permitted by protocol, they should be on a stable (scheduled) dose for at least 14 days prior to the Baseline Visit and anticipate continuing that dose through Week 16 unless a decrease in dose is warranted based on symptoms. Opioid analgesics are excluded. Note: As needed (PRN) use is not considered a stable dose, but (for example) taking a nonsteroidal anti-inflammatory drug (NSAID) 3 times per week, every week is considered a stable dose.
23. Study participant has received any live (including attenuated) vaccination within the 8 weeks prior to the Baseline Visit (eg, inactivated influenza and pneumococcal vaccines are allowed, but nasal influenza vaccination is not permitted). Live vaccines are not allowed during the study, including the SFU Period (20 weeks after the last dose of IMP).
24. Study participant has received Bacillus Calmette-Guerin vaccination within 1 year prior to IMP administration.

Prior/Concurrent clinical study experience

25. Study participant has previously participated in this study or study participant has previously been assigned to treatment in a study of the medication under investigation in this study, and received at least 1 dose of IMP (including placebo).
26. Study participant is currently participating in another study of a systemic medication under investigation, including SFU. Study participant must be washed out of the medication as indicated in Table 6–3.
27. Study participant is currently participating in another study of a topical medication under investigation, including SFU. Study participant must be washed out of the medication for 4 weeks prior to the Baseline Visit.
28. Study participant is currently, or was within the 4 weeks prior to the Baseline Visit, participating in another study of a medical device under investigation.

Diagnostic assessments

29. Study participant has laboratory abnormalities at Screening, including any of the following:
 - $\geq 3\times$ the upper limit of normal (ULN) of any of the following: alanine aminotransferase (ALT), aspartate aminotransferase (AST), alkaline phosphatase (ALP)
 - Bilirubin $>1.5\times$ ULN (isolated bilirubin $>1.5\times$ ULN is acceptable if bilirubin is fractionated and direct bilirubin $<35\%$)
 - White blood cell count $<3.00\times 10^3/\mu\text{L}$
 - Absolute neutrophil count $<1.5\times 10^3/\mu\text{L}$

- Lymphocyte count <500 cells/ μ L

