8.3.5 Pregnancy

Details of all pregnancies in female participants and female partners of male participants who become pregnant will be collected after the start of study treatment and through the SFU visit (ie, 20 weeks after last dose of IMP).

If a pregnancy is reported, the Investigator must immediately inform the Sponsor within 24 hours of learning of the pregnancy and should follow the procedures outlined in Appendix 4.

A female study participant should be withdrawn from the study as soon as pregnancy is known (by positive pregnancy test), and the following should be completed:

- The study participant should return for an early discontinuation visit.
- The study participant should immediately stop the intake of the IMP.
- An SFU Visit should be scheduled 20 weeks after the study participant has received her last dose of IMP.

Abnormal pregnancy outcomes (eg, spontaneous abortion, fetal death, stillbirth, congenital anomalies, ectopic pregnancy) are considered SAEs.

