9.8 Determination of sample size

A total of 490 study participants will be randomly assigned in a 2:2:2:1 ratio to the following treatment arms:

- Bimekizumab [REDACTED] during Initial Treatment Period (Weeks 0-16) and Maintenance Treatment (Weeks 16-48) Periods, N=140
- Bimekizumab [REDACTED] during Initial Treatment Period (Weeks 0-16), and Bimekizumab [REDACTED] during Maintenance Treatment Period (Weeks 16-48), N=140
- Bimekizumab [REDACTED] during Initial Treatment (Weeks 0-16) and Maintenance Treatment Periods (Weeks 16-48), N=140
- Placebo during Initial Treatment Period (Weeks 0-16), and Bimekizumab [REDACTED] during Maintenance Treatment Period (Weeks 16-48), N=70

The analysis of the primary efficacy endpoint and secondary efficacy endpoints are based on a comparison of bimekizumab versus placebo at Week 16, with alpha adjustment strategy as indicated in Section 9.3.1 and Section 9.3.2.

The power to detect a statistically significant difference for each of the endpoints are shown in Table 9-1. Notably, with a 2-sided significance level of 0.025, the sample size of 140:70 provides 73% power for detecting at least a difference of 1.5 (bimekizumab [REDACTED] vs placebo) for the Worst Pain change from Baseline (CFB) endpoint.

Given the high level of power for each of the primary and key secondary endpoints at the 0.025 significance level for the [REDACTED] comparison (power ≥ 0.89), and per the alpha spending strategy, there is a high likelihood that the [REDACTED] comparison of Worst Pain CFB vs placebo will be allowed to be tested against the 0.05 level of significance. The power for this latter test is 81%. The sample size is thus ultimately driven by the Worst Pain CFB endpoint. Furthermore, the randomization ratio of 2:2:2:1 has been chosen to provide study participants with a high probability (6/7 ~ 86%) of being randomized to active study drug.

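### Appendix 4 lets partner-pregnancy data collection stop for a man found to be on placebo, without excluding men who have since started bimekizumab under the Week 16 switch

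*Protocol*

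**What the plan says.** Appendix 4 asks the investigator to try to collect information on any male participant's "female partner who becomes pregnant while the male participant is in this study". It then adds two qualifiers. The first is "This applies only to male participants who receive IMP". The second is "If the study participant is later found to be on placebo, then pregnancy data collection can stop". Neither mentions the treatment period, the date of conception or whether the man has had any active drug.

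The protocol gives the treatment sequence of the placebo arm in three places:

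- Section 4.1.2: "Placebo to Week 16, continuing on bimekizumab" for Weeks 16 to 48.
- Section 4.2: "This period will also allow study participants who received placebo in the Initial Treatment Period to begin receiving bimekizumab at Week 16".
- Section 9.8: "Placebo during Initial Treatment Period (Weeks 0-16), and Bimekizumab" in the Maintenance Treatment Period, with N=70 of 490.

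Section 8.3.5 states the general rule: "Details of all pregnancies in female participants and female partners of male participants who become pregnant will be collected" from the start of study treatment through the SFU visit, 20 weeks after the last dose. It contains no exemption for placebo and refers the investigator to Appendix 4 for the procedures.

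**The concern.** A rule that ends follow-up once a man turns out to be on placebo suits a trial in which placebo participants stay on placebo. This trial has no such arm. A man randomised to placebo who remains on treatment receives bimekizumab from Week 16, so learning his randomised arm does not show that he was unexposed.

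What is at stake is completeness of safety data. Section 8.3.5 counts abnormal pregnancy outcomes as serious adverse events, and Appendix 4 has the partner followed to the outcome of the pregnancy, generally for at least 12 months after delivery. If a case is closed because of the randomised arm, the outcome of a pregnancy conceived while the father was receiving bimekizumab may never be recorded.

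**Working it through.** The protocol gives no figure to reproduce. The check sets the texts against each other and then measures how much of a placebo-arm participant's time the sentence reaches.

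**1. Does the sentence reach the Maintenance Treatment Period?** Yes. Appendix 4 covers partner pregnancies at any time while the man is in the study, and the placebo sentence adds no limit of its own.

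**2. Does the restriction to men who receive IMP remove the problem?** No. Placebo is IMP in this protocol: Table 6–1 classes it as an investigational medicinal product, and Exclusion Criterion 25 uses the words "received at least 1 dose of IMP (including placebo". The restriction therefore does not separate active drug from placebo.

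**3. When would a man be found to be on placebo?** Apart from emergency code breaks (Section 6.3.2.2), the first unblinded analysis described outside the Data Monitoring Committee comes after the last participant has completed Week 48 or discontinued (Section 9.7.2). By then every placebo-arm man who stayed on treatment past Week 16 has had bimekizumab. Because follow-up generally runs to at least 12 months after delivery, some cases could still be open.

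**4. How much time is affected?** Inputs: switch at Week 16 (Section 4.1.2); last injections at Week 46 (Section 6.1); SFU visit 20 weeks after the final dose (Section 4.1.3); entry to HS0005 at Week 48 (Section 6.8).

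- Placebo arm as a share of the trial: 70/490 = 14.3%.
- Completer entering HS0005: (48 − 16)/48 = 32/48 = 67% of his time comes after the first bimekizumab dose.
- Completer not entering HS0005: the SFU visit falls at Week 46 + 20 = 66. Time after the first bimekizumab dose is 66 − 16 = 50 weeks, and 50/66 = 76%. Of those 50 weeks, 46 − 16 = 30 are the dosing period and 20 are post-dose follow-up.

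**5. How many men?** The protocol does not plan enrolment by sex, so this is an assumption. With 25% male, the 3:1 female-to-male ratio quoted for European adults in Section 2.2, it is 70 × 0.25 = 17.5, or about 18 men. With half male, it is 70 × 0.5 = 35. These are counts of men in the arm, not of pregnancies; the protocol gives no pregnancy rate.

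**The case against.** The best defence has four parts.

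- **The wording is narrower than the randomised arm.** The sentence speaks of being on placebo, not of having been randomised to it. At Week 30 a man from that arm is on bimekizumab by design, and a code break returns treatment arm and dose, so a careful reader might see that the exemption no longer fits him. The verb is also permissive. This stands in part: loss is not certain. But the protocol nowhere adopts the narrower reading, and sites can reasonably apply either.
- **Some men never switch.** Those who stop IMP before Week 16 never receive bimekizumab, and for them the sentence works as intended. This stands, and the fix can preserve it.
- **Section 8.3.5 delegates procedure to Appendix 4.** The section could be taken to govern reporting and initial collection, and the appendix to govern when collection may end. That softens the conflict, but the unrestricted exemption remains, and Section 8.3.5 gives no hint that one exists.
- **Other routes remain.** Section 8.3.1 requires serious events thought to be associated with IMP to be reported whenever they occur, and Appendix 4 keeps a route for post-study pregnancy events judged related. These are partial backstops. They depend on the investigator learning of the event, and Appendix 4 says there is no duty to seek it out in former participants.

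A reader might go further and infer that exposed pregnancies will be misclassified as placebo cases and bias a record of paternal exposure. The documents do not support that: the protocol sets no classification rule for partner pregnancies and defines no paternal-exposure analysis. Nor does it say whether paternal dosing that begins after conception matters, so pregnancies conceived before Week 16 are not relied on here.

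**Conclusion.** The point holds as a defect of wording with a possible safety-data consequence. The sentence permits closure of partner pregnancies conceived after the father started bimekizumab, because it does not require that he never received it, and it sits badly with Section 8.3.5. It would be too strong to say that such cases will be lost, or that every participant randomised to placebo goes on to receive bimekizumab.

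The reach is one arm of seven parts (14.3% of participants) and, within it, the men only: roughly 18 to 35 under the assumed range of 25% to 50% male. For completers, 67% to 76% of their time in the study follows the first bimekizumab dose, the upper figure including 20 weeks of post-dose follow-up. Few pregnancies are to be expected. No endpoint, analysis set, error rate or power figure is affected. The correction is worth making because it is cheap and each case closed this way could be a drug-exposed one.

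**What to change.** In Appendix 4, either delete the placebo sentence or confine it to men confirmed never to have received a bimekizumab dose, that is, placebo-arm participants who stopped IMP before their first active injection. Then reconcile it with Section 8.3.5: if an exemption is kept, that section should mention it; if not, the two will agree once the sentence is gone. No new exposure-classification rule is needed.

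The cost is one sentence in an amendment, with a matching phrase in Section 8.3.5 if the exemption is kept, and follow-up of a few additional partner pregnancies through the form and partner consent that Appendix 4 already provides. That extra follow-up is the only downside.
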